#### STAFF, MEDICAL AND TECHNICAL EQUIPMENT

Hospital staff involved in stress cMRI exam is composed by: Radiologist, Cardiologist, Radiographer, Nurse. In case of necessity, first aid is guaranteed by Radiologist and Cardiologist in site, but in-Hospital Anesthetist Resuscitator is 24 hours 365 day ready to intervene for emergency related to MRI exams.

Emergency medical supplies, in recovery room: metoprololo, esmololo, nitroglycerine, adrenaline, betametasona

Medical device MRI compatibile, in scanner room: Contrast Medium pump, Dobutamine pump, cables and electrodes for four-lead VCG signal, cables and electrodes for cardiac monitoring, sat O2, heart rate and arterial blood pressure devices

Medical device not MRI compatibile, in control room: Contrast and Dobutamine pump command module, vital parameter monitor (12 lead ECG trace, blood pressure, heart rate, sat O2).

Medical device not MRI compatibile, in recovery room: vital parameter monitor (12 lead ECG trace, blood pressure, heart rate, sat O2), defibrillator

#### ADVERSE EVENTS

Potential side-effects stress-related: can start soon after Dobutamine injection and are usually over within 30 minutes. They don't usually need any treatment. They are: headache, dizziness, shortness of breath, chest pain, flushing, stomach discomfort.

Potential side-effects contrast agent-related: can partially present overlapping features with side-effects stress-related. They are: headache, dizziness, shortness of breath, chest pain, flushing, nausea, injection site pain, injection site coldness, burning sensation, feeling cold, rash, somnolence, fatigue, dizziness, vomiting, pruritus, paresthesia, dysgeusia, pain in extremity, anxiety, hypertension, palpitations, oropharyngeal discomfort.

Potential stress-related adverse events are:

Myocardial ischaemia: fatal cardiac arrest, life-threatening ventricular arrhythmias, and myocardial infarction may result from the ischaemia induced by pharmacologic stress agents.

Sinoatrial and atrioventricular nodal block: may depress the sinoatrial (SA) and arterioventricular (AV) nodes and may cause first, second or third-degree AV block, or sinus bradycardia.

Hypotension: may induce arterial vasodilation and hypotension. The risk of serious hypotension may be higher in patients with autonomic dysfunction, hypovolemia, left main coronary artery stenosis, stenotic valvular heart disease, pericarditis or pericardial effusions, or stenotic carotid artery disease with cerebrovascular insufficiency.

Bronchoconstriction: may cause bronchoconstriction and respiratory compromise. For patients with known or suspected bronchoconstrictive disease, chronic obstructive pulmonary disease (COPD) or asthma, appropriate bronchodilator therapy and resuscitative measures should be available prior to administration.

Potential contrast agent-related adverse events are:

Bradycardia, tachycardia, arrhythmia, anaphylactoid reactions including cardiac arrest, respiratory arrest, cyanosis, pharyngeal edema, laryngospasm, bronchospasm, angioedema, conjunctivitis, ocular hyperemia, eyelid edema, lacrimation increased, hyperhidrosis, urticarial, coma, convulsion, syncope, presyncope, parosmia, tremor.

During our study, all side effects and adverse events will be recorded in the registry for further analysis.

Adverse events will be coded using the MedDRA dictionary that provides the primary system organ class and preferred term information. All other information collected (e.g. severity, relationship to study treatment) will be tabulated and listed as appropriate. Adverse events will also be summarized by SMQ.

### OTHER EXAMS

**Stress Cardiac Transthoracic Ultrasound** is performed by a Cardiologist with at least 5 years of experience in Congenital Heart Disease Ultrasound, without knowing the result of Cardiac MRI, in a window time of 3 month before or after Cardiac MRI. Stress Cardiac Transthoracic Ultrasound exam protocol includes evaluation of origin and proximal pathway of coronary arteries, left chamber function, wall motion

abnormalities, systolic wall thickening, abnormal echogenicity of myocardium. Results are reported according to 17 segments classification (AHA). Cardiologist analyses right ventricle outflow tract (RVOT), main pulmonary artery and branch pulmonary arteries diameter, morphology and flow. The greatest velocity detected by echocardiography across the pulmonary valve, pulmonary trunk, or pulmonary branches was used in the analysis as an index of RVOT obstruction.

**Exercise test** is performed by a Cardiologist with at least 5 years of experience in Congenital Heart disease CPEX, without knowing the result of Cardiac MRI, in a window time of 3 month before or after Cardiac MRI. The peak exercise oxygen uptake ( $VO(2)$ ), and heart rate were recorded and are expressed as the percentage of predicted values.

**Coronary Angiography** is performed by a Interventional Cardiologist with at least 5 years of experience in Congenital Heart disease Angiography, without knowing the result of Cardiac MRI, in a window time of 3 month before or after Cardiac MRI. Exam protocol includes evaluation of origin and pathway of coronary arteries, RVOT morphology and pressure, main pulmonary artery and pulmonary branches morphology, diameter and intraluminal pressure.

ECG, Stress Cardiac Ultrasound, Exercise test, Coronary angiography are performed the same day.

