## 1. BACKGROUND

Transposition of the great arteries, the most common cyanotic congenital heart lesion found in neonates, accounts for 5%–7% of congenital cardiac malformations.

Arterial switch surgery is now the treatment of choice for transposition of the great arteries. In this procedure, the aorta and main pulmonary artery are transected, switched, and re-anastomosed to the correct ventricle. The coronary arteries and a small portion of aortic sinus are excised when the aorta is transected and are re-implanted once the aorta is connected to the left ventricular outflow tract.

Most complications and mortality occur within the first year of life, and are secondary to myocardial ischemia or infarction associated with relocation of the coronary arteries at surgery. Nonetheless, follow-up studies have revealed a significant prevalence (7-8%) of coronary stenosis, occlusions and late death in an otherwise symptom-free patient population.

Other pathologic condition affecting coronary arteries during pediatric age, with a lower incidence than transposition of coronary arteries, are: Kawasaki disease, primary dilatative cardiomyopathy of undetermined nature, ALCAPA syndrome and other coronary artery anomalies of origin and pathway, coronary fistula, coronary atresia, familial hypercholesterolemia, bicuspid aortic valve, chest pain or dispnea related to exercise of suspected coronary nature.

Following current practice, pediatric patients affected by or with suspected coronary artery disease undergo to Exercise Test, Eco stress and Coronary Angiography. While coronary angiography (CA) is considered the gold standard for detection of coronary lesions necessitating possible interventions, CA is a invasive and x-ray exposing technique which cannot be included in regular follow-up in asymptomatic children.

Cardiovascular Magnetic Resonance imaging (cMRI) provides both morphologic and functional information that can be decisive in the treatment of neonates and infants with congenital heart disease. Thanks to its non-invasiveness and lack of ionizing radiation, cMRI is now becoming a major imaging tool in pediatric congenital heart disease.

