**Primary Endpoint:**

- Agreement of results between stress cMRI and the current practice constituted by Exercise test, Stress Cardiac Ultrasound and Invasive Angiography.

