### 4. STUDY PROCEDURES

The study population will be recruited, over a period of approximately 24 months, from children attending the ward and the outpatient clinics of the cardiologic paediatric unit, in accordance with the following inclusion criteria.

4.1 Inclusion Criteria are: Between 8 and 18 years-old patients symptomatic and non, with suspected or previously diagnosed coronary arteries disease: Coronary artery re-implantation after arterial switch, ALCAPA Syndrome, other anomalies of origin or pathway, replacement of aortic valve with pulmonary autograft (Ross procedure), Kawasaki disease, primary dilatative cardiomyopathy, coronary atresia, familial Hypercholesterolemia, bicuspid aortic valve, chest pain, exertional dyspnea of suspected coronary artery nature, coronary artery fistula.

4.2 Exclusion criteria are: General contraindication to MRI (non MRI compatible device: vascular clips, foreign bodies, coronary and peripheral artery stents, aortic stent grafts, prosthetic heart valves and annuloplasty rings, cardiac occluder devices, vena cava filters and embolisation coils, haemodynamic monitoring and temporary pacing devices, haemodynamic support devices, permanent cardiac pacemakers and implantable cardioverter-defibrillators, retained transvenous pacemaker and defibrillator leads, cochlear implants, claustrophobia, pregnancy and postpartum), contraindication to contrast agent (renal insufficiency, hypersensitivity to the Dotarem active substance or to any of the excipients:), contraindication to stress agent (hypersensitivity to Dobutamine active substance or to any of the excipients; severe arterial hypertension ( $\geq 220/120$  mmHg), unstable angina pectoris, significant aortic stenosis, complex cardiac arrhythmias including uncontrolled atrial fibrillation, hypertrophic obstructive cardiomyopathy, myocarditis, endocarditis, pericarditis, uncontrolled congestive heart failure, previous manifestations of hypersensitivity to dobutamine, refuse to join the protocol and relative off-label procedures.

A total number of 15 patients fitting the above criteria is the target of our study.

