### 4.3 Study Procedure

#### METHOD

- 1) Ask for permission of local ethic board
- 2) Identify all patients in follow-up at Gaslini Institute, with suspected or previously diagnosed coronary arteries disease
- 3) Patients selection based on inclusion criteria
- 4) Patient call and first clinical visit, which includes explanation of research protocol and consent form signature
- 5) Stress CardiacMRI scan, ECG and Stress Cardiac Ultrasound exam, Exercise Test, Coronary Angiography.

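### The conventional tests are masked to the cMRI result, but the cMRI read is not masked to theirs, although they may come first; this can bias the primary kappa towards agreement

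*Protocol*

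**What the plan says.** The primary endpoint (section 2) is "Agreement of results between stress cMRI and the current practice constituted by Exercise test, Stress Cardiac Ultrasound and Invasive Angiography". Section 4.4 analyses it with kappa and grades the result in fixed bands.

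The masking rule stands under Other Exams in section 4.3. Stress ultrasound, exercise test and coronary angiography each have a paragraph, and each is to be done "without knowing the result of Cardiac MRI, in a window time of 3 month before or after Cardiac MRI". The subsection ends: "ECG, Stress Cardiac Ultrasound, Exercise test, Coronary angiography are performed the same day". Step 5 of the Method list names the examinations together, "Stress CardiacMRI scan, ECG and Stress Cardiac Ultrasound exam, Exercise Test, Coronary Angiography", without prescribing a sequence.

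On the cMRI side, section 4.3 covers preparation, sequences and staff. The staffing statement is "Hospital staff involved in stress cMRI exam is composed by: Radiologist, Cardiologist, Radiographer, Nurse". It does not say who interprets the images or what that person may know.

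Three further statements bear on what a reader might already know. Method step 2 is "Identify all patients in follow-up at Gaslini Institute, with suspected or previously diagnosed coronary arteries disease". The inclusion criteria (section 4.1) begin "Between 8 and 18 years-old patients symptomatic and non, with suspected or previously diagnosed coronary arteries disease". The Background says: "Following current practice, pediatric patients affected by or with suspected coronary artery disease undergo to Exercise Test, Eco stress and Coronary Angiography".

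**The concern.** In an agreement study each method should be read without knowledge of the other. This protocol sets masking in one direction only, and that direction does not cover one of the two test orders it allows.

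If the conventional work-up is finished before the scan, information can flow only from those tests to the cMRI reader, and nothing in the protocol stops it. A reader who knows that the angiogram was normal, or that the stress echo showed a wall motion abnormality, may settle an equivocal image in line with it. Discordant pairs then become concordant and kappa rises.

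The Background says the team hopes to replace the conventional work-up with stress cMRI if the results support it, so the bias would favour the hoped-for conclusion. Statistical adjustment alone cannot remove it, and a larger sample would not reduce it. A masked re-read of stored images could remove it, but the protocol does not provide for one.

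**Working it through.** The protocol gives no expected kappa, prevalence, sensitivity or specificity, so there is no figure to reproduce. The check is a reading of the text, followed by an illustration on assumed inputs.

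**Step 1. Who is masked to what**

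| Examination | Masked to the other side? | Timing |
|---|---|---|
| Stress ultrasound | Yes, to cMRI | Up to 3 months before or after cMRI |
| Exercise test | Yes, to cMRI | Same |
| Coronary angiography | Yes, to cMRI | Same |
| Stress cMRI read | Nothing stated | – |

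Three of the three tests in the primary endpoint carry the masking phrase; the cMRI read carries none. I looked in the Method list, exam preparation, MRI protocol, staffing, Other Exams and section 4.4.

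**Step 2. What each order allows**

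- *cMRI first.* The rule works: the conventional operators must not know a result that exists.
- *Conventional tests first.* They share one day, so the whole study comparator can be complete up to 3 months before the scan. When they are performed there is no study cMRI result to withhold. The masking that would matter is that of the cMRI reader, and it is not stated.
- *Either order.* Patients come from follow-up, may already be diagnosed, and by the Background's account undergo these same tests in current practice. Some may have earlier results of the same kind as the comparator. The protocol does not say how many, or whether the cMRI reader sees them.

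**Step 3. How many patients**

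The target is 15 (section 4.2) and the order is open. The number with the study comparator known before the cMRI read can be anything from 0 to 15.

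**Step 4. Illustration on assumed inputs**

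Let a = both positive, b = cMRI positive only, c = conventional positive only, d = both negative, n = 15. Then po = (a+d)/n, pe = [(a+b)(a+c) + (c+d)(b+d)]/n², and kappa = (po − pe)/(1 − pe).

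Assume 6 conventional positives and four discordant reads, and move discordant cMRI reads to match the conventional result:

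| Reads moved | a/b/c/d | po | pe | kappa | Band in section 4.4 |
|---|---|---|---|---|---|
| 0 | 4/2/2/7 | 11/15 | 117/225 | 0.44 | moderate |
| 1 (from b) | 4/1/2/8 | 12/15 | 120/225 | 0.57 | moderate |
| 1 (from c) | 5/2/1/7 | 12/15 | 114/225 | 0.59 | moderate |
| 2 (one of each) | 5/1/1/8 | 13/15 | 117/225 | 0.72 | substantial |
| 3 (two from b, one from c) | 5/0/1/9 | 14/15 | 120/225 | 0.86 | almost perfect |

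First row: (0.733 − 0.520)/(1 − 0.520) = 0.44.

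Expected kappa was also computed for assumed prevalences of 0.08, 0.20 and 0.40, crossed with sensitivity/specificity pairs 0.80/0.80, 0.70/0.90 and 0.85/0.85:

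| Share of discordant reads moved | Range of kappa |
|---|---|
| 0 (masked read) | 0.31–0.69 |
| 25% | 0.41–0.77 |
| 50% | 0.54–0.84 |

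A rise is expected by construction. The tables show how few reads are needed to change band at n = 15; they do not show that the bias will occur.

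**The case against.** The strongest reply is that the protocol says nothing false here. It simply does not describe the cMRI read, and the rules may be on the attached data collection sheet (section 5.1), which I have not seen. That limits confidence, and the point falls away if the sheet masks the read. But reader masking is study conduct, and this protocol chose to fix it in its procedures for every comparator in the primary endpoint. Fixing it on one side only, with the order left open, is a flaw in the text as written.

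Second, the existing masking is not always idle when the conventional tests come first. The protocol does not date their reporting, so a report written after the scan would still benefit. Some patients may also have had an earlier routine cMRI. Both points are fair, but neither protects the cMRI reader.

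Third, the route through earlier routine results is conjecture and can be closed only in part, since patients are selected on known diagnoses and operations. That stands; it is secondary, and the main point does not need it.

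Fourth, step 5 lists the cMRI first, and masking the comparators makes most sense in that order, so few patients may be affected. This is suggestive only, because the window expressly allows the reverse order. The range of 0 to 15 reflects that openness and is not an estimate.

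Fifth, kappa will be imprecise in a pilot of 15. In the illustration the simple standard error is √[0.733 × 0.267/(15 × 0.48²)] = 0.24, a rough 95% interval of −0.02 to 0.91, and all the shifted values lie inside it. That limits what the pilot can show, but imprecision does not excuse a bias with an expected direction.

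**Conclusion.** The concern holds. As written, the protocol lets the cMRI reader know the full comparator of the primary endpoint before reading the scan. The expected direction is towards agreement; true change in disease over a gap of up to 3 months would act the other way.

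The size cannot be computed from the protocol. It depends on how many patients have the conventional tests first, whether the reader sees those results, and how far they sway the read. Under the assumed 15-patient table, two swayed reads lift kappa from moderate to substantial and three to almost perfect.

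The conclusion assumes that the unseen data collection sheet does not already mask the cMRI read. Confidence is medium. This should be corrected, and the correction is cheap.

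**What to change.** Add to the Cardiac MRI Protocol part of section 4.3:

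> The study cMRI images are interpreted by a member of the existing staff who did not perform that patient's conventional tests and has no access to their results or, as far as practicable, to earlier routine coronary test results. Any such result known to the reader beforehand is noted on the form. The cMRI result is recorded, dated and locked before the conventional results are disclosed to the reader. The order of the tests is recorded for each patient. This masking applies to the study image read only, not to staff supervising the exam or to access to information needed for safety.

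The essential part is masking to the study's own conventional results and locking the read. The notes on order and on results already known let the final report show how far masking was achieved. If the data collection sheet already contains such a rule, the protocol need only state it.

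The cost is a locked, dated report form and minor scheduling. By role a suitable reader exists: the cMRI team includes a radiologist, while all three conventional tests are assigned to cardiologists. The protocol lists roles and not numbers, so the site must confirm that a reader without access to the conventional results is available.

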#### 4.4 STATISTICAL CONSIDERATIONS

Data will be described as means, standard deviation (SD) and medians with a range for continuous variables, while absolute and relative frequencies will be used for categorical variables.

Categorical data will be compared by chi-square test or by Fisher's exact test in case of expected frequencies  $<5$ . Comparisons of quantitative variables will be performed by Student's t test for paired data or Wilcoxon test. Concordance between MRI- and traditional test will be determined by the Kappa statistical method as described by Landis and Koch, and  $\kappa$  will be interpreted as follows:  $\kappa$  value of 0 indicates poor agreement;  $\kappa$  value of 0.01–0.20, slight agreement;  $\kappa$  value of 0.21–0.40, fair agreement;  $\kappa$  value of 0.41–0.60, moderate agreement;  $\kappa$  value of 0.61–0.80, substantial agreement; and  $\kappa$  value of 0.81–1; almost perfect. p-value less than 0.05 will be considered statistically significant, and all p-values will be based upon two tailed tests. Statistical analysis will be performed using SPSS for Windows (SPSS Inc, Chicago, Illinois USA).

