### 3. STUDY DESIGN:

Mono-centre, pilot, prospective interventional study.

cMRI exam with injection of Contrast Medium is considered a safe and robust technique to study congenital heart disease in pediatric patient. At Gaslini Institute, our Cardio-Radiology team accounts for more than 1000 cMRI exams of congenital heart disease performed in pediatric patients, without major adverse events reported.

Furthermore, in our centre, Dobutamine is routinely administered to all patients during diagnostic stress procedures (Stress Cardiac Ultrasound and Invasive Angiography), which correspond to the current practice to investigate coronary arteries anomalies according to international guidelines.

Therefore, stress cMRI with Dobutamine stress agent (stress cMRI), from a procedural perspective, represent the combination of two orders of exams routinely performed (cMRI and stress diagnostic series of exams) without additional risk for the patient, but with the advantage of non-invasiveness and lack of radiation, less laborious for the Patient and less expensive for the Healthcare.

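### Section 4.4 names only unpaired tests for categorical data that are largely within-patient, and reads the primary kappa by bands whose neighbours 15 patients cannot separate

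*Protocol*

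**What the plan says.** The study is a "Mono-centre, pilot, prospective interventional study" with no parallel arm described. Section 4.3 (Method) lists the examinations for each patient: "Stress CardiacMRI scan, ECG and Stress Cardiac Ultrasound exam, Exercise Test, Coronary Angiography". The target is stated in section 4: "A total number of 15 patients fitting the above criteria is the target of our study".

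The primary endpoint in section 2 is "Agreement of results between stress cMRI and the current practice", the latter being exercise test, stress ultrasound and angiography.

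Section 4.4 then fixes three things:

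- Categorical data: "Categorical data will be compared by chi-square test", or Fisher's exact test where expected frequencies are below 5. No paired categorical test is named.
- Quantitative data: Student's "t test for paired data or Wilcoxon test".
- Primary agreement: "Concordance between MRI- and traditional test will be determined by the Kappa statistical method", and the value of kappa "will be interpreted as follows", followed by the Landis-Koch bands (0.01–0.20, 0.21–0.40, 0.41–0.60, 0.61–0.80, 0.81–1). No success threshold is attached to a band.

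Significance is two-sided at 0.05. Section 4.4 does not say which categorical comparisons it has in mind, nor whether the unit for kappa is the patient or the myocardial segment.

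**The concern.** **Categorical tests.** Section 4.4 allows for pairing in quantitative data but not in categorical data. Several comparisons that the protocol sets up would be within-patient if analysed as categories. Examples are stress cMRI against cMRI (section 2, Secondary Objectives) and symptoms before and after the stress agent (section 4.3, Cardiac MRI Protocol). On a cross-table of paired results, chi-square or Fisher asks whether the two readings are associated. It does not ask whether one method, or one time point, gives more positives. A one-directional shift can go unflagged, and a small p-value can accompany complete disagreement.

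**Reading of kappa.** The bands are about 0.20 wide and are applied to the point estimate. With 15 patients the sampling error of kappa is wider than a band, so the label for the primary endpoint can easily be a neighbour of the true one. Section 1 says that stress cMRI may replace the current work-up if the results support it, so an unqualified label could carry more weight than the data allow.

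**Working it through.** The protocol gives no derivation of its 15 patients, so there is no stated figure to reproduce.

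**Inputs.** From the protocol: n = 15 (section 4); two-sided 0.05 and the band limits (section 4.4). Assumed: one binary result per patient and method; equal positive rates P on both methods, from 20% to 50%; true kappa K as shown. Tables are written a/b/c/d = both positive, first method only, second method only, both negative.

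**1. Fisher against exact McNemar at n = 15**

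Table 4/6/0/5 (margins 10/5 and 4/11):
- Fisher: the outcomes no more probable than the one observed have weights 210 + 100 + 5 out of C(15,4) = 1365, so p = 315/1365 = 0.23.
- Exact McNemar: six discordant pairs, all one way, so p = 2 × (1/2)^6 = 0.031.
- Kappa: observed agreement 9/15 = 0.600; chance agreement (10×4 + 5×11)/225 = 0.422; kappa = (0.600 − 0.422)/(1 − 0.422) = 0.31.

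Table 0/10/5/0 (the methods disagree in all 15 patients):
- Fisher: p = 1/C(15,5) = 1/3003 = 0.0003.
- Exact McNemar, split 10 to 5: p = 0.30.
- Kappa: chance agreement (10×5 + 5×10)/225 = 0.444; kappa = (0 − 0.444)/(1 − 0.444) = −0.80.

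So Fisher misses a one-directional shift in the first table and is strongly significant at zero agreement in the second. McNemar does not measure agreement either, so it supplements kappa and does not replace it.

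Of the 756 possible tables with n = 15 and no empty margin, 150 have exact McNemar p<0.05. The largest kappa among them is 0.308. Where kappa is also reported, it would therefore already be low.

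**2. Precision of kappa at n = 15**

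At P = 50% the large-sample standard error is √((1 − K²)/n). For K = 0.70 it is √(0.51/15) = 0.184, a 95% half-width of 1.96 × 0.184 = 0.36. The general formula gives standard errors of 0.20 at P = 30% and 0.23 at P = 20%, with half-widths of about 0.40 and 0.46. The bands are about 0.20 wide.

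**3. Chance that the label is the true band**

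The cell probabilities are P² + K·P(1−P) for both positive, P(1−P)(1−K) for each discordant cell, and (1−P)² + K·P(1−P) for both negative. The exact multinomial probabilities of all tables were summed, with kappa rounded to two decimals.

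| True kappa | True band | P = 20% | P = 33% | P = 50% |
|---|---|---|---|---|
| 0.30 | fair | 20% | 29% | 31% |
| 0.50 | moderate | 30% | 36% | 39% |
| 0.70 | substantial | 27% | 29% | 32% |
| 0.85 | almost perfect | 63% | 69% | 68% |
| 0.90 | almost perfect | 74% | 82% | 82% |

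A true kappa of 0.30 is labelled *moderate* or better in 33% to 37% of trials. A true kappa of 0.50 is labelled *substantial* or better in 27% to 33%.

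**4. Sensitivity to the unit**

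With 17 segments × 15 patients = 255 independent units, the half-width at K = 0.70 and P = 50% would be 0.36 × √(15/255) = 0.09. With an assumed within-patient correlation of 0.1 to 0.3, the design effect 1 + 16 × correlation is 2.6 to 5.8. The half-width is then 0.09 × √2.6 = 0.14 to 0.09 × √5.8 = 0.21.

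**The case against.** - **The text never assigns chi-square or Fisher to cMRI against the conventional tests.** That stands: section 4.4 gives this comparison to kappa. A reader might infer that the primary analysis ignores the pairing. It does not, because kappa uses the paired table. The point is limited to supporting comparisons, which the text does not spell out, and chi-square/Fisher is valid between patient groups such as symptomatic and asymptomatic children.
- **The label is not always unreliable.** That stands too. A reader might infer that at n = 15 it is wrong more often than right whatever the truth. At true kappa 0.85 or 0.90 it is right in most trials, and high agreement is the range that matters most for replacing current practice. A true kappa of 0.30 is labelled *almost perfect* in only 1% to 4% of trials. What fails is the separation of neighbouring bands at lower to substantial agreement.
- **A *moderate* label could hide missed positives.** It can: 3/0/4/8 has kappa 0.44 while the first method misses 4 of 7 positives. But only 3 of the 70 possible *moderate* tables have more than half of the positives missed. That is a count of tables, not a probability, and does not show that it is likely.
- **A segment-level analysis would be more precise.** It would, and the unit is not stated. However, segment reporting is given only for stress ultrasound (section 4.3, Other Exams), so it does not settle the comparison with the whole conventional work-up.
- **This is a pilot, and intervals and percent agreement can be left to a statistical analysis plan.** The pilot label does excuse a small n, and missing intervals alone would be no finding. But section 4.4 positively names the tests and the way kappa is to be read, and those stated choices can be improved.

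**Conclusion.** The point holds and is minor.

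The stated categorical tests do not answer a within-patient question of difference, and at n = 15 their verdict can differ from that of exact McNemar (0.23 against 0.031). The harm is confined to supporting comparisons.

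For the primary endpoint, the band label matches the true band in 20% to 39% of trials at true kappa 0.30, 0.50 or 0.70, against 63% to 82% at 0.85 to 0.90. These figures rest on one binary result per patient, equal positive rates of 20% to 50% on both methods, and 15 evaluable patients. Because no success threshold is tied to a band, the issue is how the result will be described. A reader might infer a faulty decision rule, but the protocol contains none.

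**What to change.** Amend section 4.4 in two or three sentences:

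1. State which categorical comparisons are within-patient and use the exact McNemar test for the binary ones. Keep chi-square/Fisher for between-patient groups.
2. Base the reading of the primary result on kappa with its 95% confidence interval, together with positive and negative percent agreement with exact intervals. State the unit of analysis.
3. Say that the Landis-Koch bands are descriptive only.

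For table 3/0/4/8 the report would then show kappa 0.44 (0.06 to 0.83), positive agreement 3/7 = 43% (10% to 82%) and negative agreement 8/8 = 100% (63% to 100%), where the band alone would say *moderate*.

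The cost is a short text change and trivial analysis work, with no extra patients or data. There are two downsides. The intervals will be wide. Exact McNemar also needs at least six discordant pairs to reach p<0.05 (6–0 gives 0.031, 5–0 gives 0.0625), so a non-significant result must not be read as agreement.
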